We propose a longitudinal of 300 RA (150 with and 150 without EI), to test for (*primary outcome*) change in CVRA at 2-3 months following web-based EI, and compare that with CVRA changes among RA patients without IE. The proposed secondary outcomes will explore the rates of CVRS via medical chart review among RA patients with and without IE. Consenting participants (RA patients (n=300) and PCHPs) will have (a) baseline survey on CVRA, followed by a short EI delivered via YouTube video (n=150), followed by immediate and 2-3-month follow up surveys, to quantitate changes in CVRA, (b) a medical record review of participating RA patients (n=300) will be undertaken (records from preceding one year duration) and at 12 months (after baseline visit) to determine the changes in CVRA evaluations and the EI. Care will be taken to avoid enrollment of PCHPs providing care to RA patients not in the EI arm, to not confound the results.

Educational approach is discussed in the section I. We expect to reach out to 600 RA patients at RUMC and JSH, with the goal of recruiting 300 RA patients over 12 months. This screening-to-enrolment ratio is consistent with previously observed 10:9 ratio for survey-based one-visit

studies at RUPC and JSH. We expect to reach our expected goal of 300 RA patients even if screening-to-enrollment ratio erodes to 10:5. Sample size calculation: To show an improvement of 20% in overall CVRA, with 90% power and 0.05% alpha error, we need 127 RA patients in each group.

H. Innovation: We did not find on our review of current medical literature (PubMed and Ovid Medline) using the search terms "Rheumatoid arthritis" and "educational intervention" and "web" for any existent EI studies that study patient-PHCP CVRA or utilize a YouTube based EI to improve CVRA. Furthermore, use of patient-PHCP dyad for CVR EI has not been reported. We feel confident that our study idea is original and has significant advantages over existent methods as it is easier, quicker and has significant potential applications. The you tube video EI if successful can be offered through National organizations e.g. American College of Rheumatology or Arthritis Foundation; and can be made available to large numbers of RA patients worldwide with less resources utilization and advantages of privacy, flexibility and access to users.

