Phase 1/Aim1: Development and implementation of a 30- minute web based (You Tube) educational intervention to improve patient-physician awareness for CVR in RA.	Pre testing and Credibility surveys to evaluate the feedback provided by the patients- PHCP on the need for the study, and on the ease, content and understandability, relevance of the educational module.	We expect the intervention module to be feasible and credible (user friendly, content, understandibility and relevant) in improving knowledge of CVR in RA	No educational interventions targeting patient- PHCP CVR awareness are yet available for RA patients.	
Aim 2A: To compare changes in CVRA in RA patients (a) after web-based EI (b) with and without web-	(a) Overall CVRA	We expect a 20% increase in CVRA at 2-3 months post El	Patients have poor knowledge in general about overall CVR, in women and in RA. No studies exist yet in the United States in RA ascertaining patient and PHCP awareness of CVR, despite the documented increased risk of CVD in RA.	
based El	(b) Overall CVRA	Change in overall CVRA will be significantly greater among RA with EI than non EI	There is a lack of knowledge among PHCP about CVD risks among women and RA. No studies exist yet in the United States in RA ascertaining patient- PHCP awareness of CVR, despite the documented increased CVR in RA.	
Aim 2B: To explore changes in cardiovascular risk screening (CVRS) at the primary health care visits among RA patients with and without EI.	Prevalence rates of relevant CVR assessment performed by PHCP among RA patients (with and without EI)	Prevalence rates of CVRS at 1 year follow up will be significantly higher among RA patients post EI as compared to baseline. Change in prevalence rates of CVRS at 1 yr follow up will be	RA patients PHCP may not be clear on whose responsibility is it for CVR assessment, when RA patient sees ≥ 2 physicians. Status of CVRS, lipid screening or treatment of dyslipidemia in RA is far from optimal, even in Medicare age group patients. There is a lack of knowledge in general about CVD risks in women and their physicians. No studies exist yet in the United States in RA ascertaining patient-PHCP awareness of CVR,	

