meeting the following criteria (i) Diagnosed with RA with following criteria: Inflammatory symmetric polyarthritis of \geq 6 weeks, with physician documented synovitis in medical records (past or current) consistent with RA, with or without rheumatoid factor, anti cyclic citrullinated peptide or radiologic evidence of RA. Exclusion of another etiology for above. (ii) Receipt of care by rheumatologist at either RUMC or JSH. This will allow us access to full medical records to correctly gauge the prevalence of CVRS. (iii) Informed consent. *B. PHCP*: (i) Physicians providing primary care to the RA patients recruited for this study for the El group. Definition of PHCP has been previously provided (section F), (ii) Informed consent (iii) Not providing PHCP to RA patients in the non-El group.

1.2. *Methods: 1.* Education intervention development phase: The primary outcome of the intervention development phase will be patient-centered EI video and PHCP-centered education EI to increase CVRA in RA. The interdisciplinary study team will develop a multi-level web-based EI for CVRA targeted to RA patients and their PHCPs. This team will consist of 3-6 RA patients and the panel of experts in rheumatology, preventive cardiology/endocrinology, and experimental health and social psychology. To improve overall RA patient outcomes, our educational approach for the web-based EI is specifically aimed at changing the knowledge, and thus health behaviors of RA patients and their PHCP.

Educational Approach: In the **development of the web-based EI** (Table 1, Figure 1), we will utilize credible, useful, innovative educational platform and input from opinion leaders in the therapeutic areas. All educational content will be learner centric in approach, language and content (Table 2). Content appropriateness of the tailored intervention will be verified by the health experts. Processes of change will be focused on increasing RA patients or their PHCP CVRA in general and in RA, and increasing their awareness of the need for change. This 20-30 minute You Tube EI video will be developed using scientifically researched content (Table 2).

	Table 2: Develo	opment of Content for Educational web-based Intervention
Audience	Major Areas in Content Develo	Key Features
Patients	1) What is CVD and CVD in USA	Definition of CVD, Leading cause of death
	2) CVD in Women	Leading cause of death in women

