	3) Traditional CVR factors	Modifiable and Non Modifiable
	4) Autoimmune diseases and CV	American Heart Association Guidelines (AHA) for CVR in women.
	5) RA and CVD	Major cause of mortality in RA
	6) RA specific CVR factors	Disease activity, duration, medications
	7) Suggested CVRS applicable to	US preventive services task force guidelines, National Cholesterol Education Program guidelines, EULAR guidelines
	8) Patients role in CVRS	For traditional CVR factors, contact PHCP; For RA factors contact Rheumatologist
РНСР	1) CVD in USA	Burden of CVD in US
	2) CVD in Women	Morbidity and mortality with CVD among women, Under recognized
	3) Traditional CVR factors	Framingham Risk factors and calculations
	4) Autoimmune diseases and CV	American Heart Association Guidelines (AHA) for CVR in women, especially RA, Lupus and psoriatic arthritis. Suggested adjustment for RA
	5) RA and CVD	Review of evidence based literature for RA and CVD
	6) RA specific CVR factors	Review of literature on RA associated factors associated with CVD eg inflammation
	7) Suggested CVRS in RA	Gaps in CVRS in RA, US preventive services task force guidelines, National Cholesterol Education Program guidelines, EULAR guidelines
	8) PHCP role in CVRS	For traditional CVR factors, contact PHCP; For RA factors contact Rheumatologist, PQRI

The finalized EI will be pretested among 5-10 RA patients and Physicians. Table 3 summarizes the way the planned methods address the established needs or identified gaps.

Table 3: Approach to	the needs and identified gaps in ca	rdiovascular risk awareness.
Established Need/Gap	Type of need/ Gap	Adressal of need/Gap through this study
Women have unique CVD risk Factors	Knowledge	Autoimmunity eg RA is a risk factor for CVD in women. We would foster education about this among women with RA and their PHCP.
The death rates from CAD in US women 35-54 yrs of age are increasing	Knowledge, Performance	By educating RA patients and PHCP about RA and CVD risk, especially in women, we expect PHCP and patients to partner CVRS in RA women, and decrease mortality.
Major cause of mortality in RA is CVD	Knowledge, Performance	By educating RA patients-PHCP about RA and CVR, we expect thenm to partner to screen for CVR in RA , and decrease mortality. Also by documenting poor CVRA among RA Patients and physicians, guidelines could be developed to ascribe responsibility and develop quality improvement initiatitives through physician reimbursements.

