Participant	Procedure	Baseline (Day 0)	FU 1 (Day 0)	FU 2 (2-3 month)	FU (1 Year)
Focus Group (RA) n=5	Informed Consent	٧			
	Demographics	V			
	Interviews	٧			
	CVR Survey	V.	1253		
	Honorarium (\$25)	V	Region		
Pretest (RA) n=10	Informed Consent	V	and the second s		
	Demographics	V	- The		
	You Tube Video	V	10	(a)	
1.4	Interviews	V			
4	CVR Survey	V		2	
14	Honorarium (\$25)	V		30	
RA patients n=150 (EI)	Informed Consent	V		第	
1. Sec. 1.	Demographics	V		14 C	
E.	CVR Survey	V (in person)	√ (In person)	v (In person)	
80	You Tube Video	V		22	
1	Honorarium (\$25)	٧		V	
23	Medical Chart	٧	1 N	2	V
RA Patients n=150 (non El)	Informe d Co nsent	Drove	ed /	1	
22	Demographics	V	11	13	
24	CVR Survey	√ (In person)	1	V (In person)	
14	You Tube Video		1	5	
	Honorarium (\$25)	٧	14	V	
	Medical Chart Review	V	AT THE A		٧
РНСР	Informed Consent	V	- Tele		
n=50	Demographics	V	[name]		
	CVR Survey	√ (Email)	V (Email)		
	You Tube Video	V	-		

I. Pilot-testing phase procedures are summarized in Table 4 and figure 1.

Assessment of CVRA in Patients: After informed consent, each participant will be assigned a unique study number, which will be used to pair data from the pre- and post-intervention visits. Participants will be given an online survey to fill to assess their CVRA (*Baseline Patient survey*). A You Tube video will be shown to the patient on a tablet or a computer screen. The video recording will be of 20-30 minutes duration to avoid attention fatigue. Immediately after viewing the video, each patient will be given the CVRA online survey (*Follow up Patient survey* 1). An exit online credibility survey will be used to gather feedback on credibility (user-friendliness, content, understandability, and relevance), barriers experienced in using the webbased intervention and any suggestions (open-ended). To assess retention of knowledge, between 2-3 months after the baseline visit the second post-intervention assessment (*Follow up Patient survey* 2) using the same CVRA survey will be administered online. Follow up survey

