Rates for CVRS at baseline and one year later for all RA patients (with and without EI) will be determined using a checklist.

I.7. Proposed Analyses: (Table 1) SPSS software will be used for data analyses. Data distribution will be evaluated. Standard descriptive statistics will be used to analyze (a) patient characteristics: demographics, socioeconomic status, RA disease pertinent information; and (b) PHCP characteristics: demographics, type of physician and practice, board certification status, and annual count of RA patients. Comparison between demographics and disease characteristics of RA patients with and without EI will be conducted using chi square and t test analysis.

I. Intervention development phase

Aim 1. Qualitative analyses will be used to gather data about the content, relevance, ease-ofuse, credibility and delivery of the educational materials. This data will be used to refine the intervention. Descriptive EI fidelity monitoring data analysis will be undertaken (mean duration (Patient or PHCP) engagement YouTube EI video, completion of CVRA at follow up 1 for patients and PHCPs, and credibility survey data). Latter data will evaluate the need, ease, content and understandability, relevance of the EI.

Engagement of audience will be judged through observation of body language RA patients during the entire study. In addition, feedback on the credibility of the intervention is being sought from both the patients and PHCP to establish its user-friendliness, content, relevance and understandability. Moreover, special efforts have been undertaken to limit survey burden and limit the duration of the EI to allow for full engagement of the participants. We feel that the technology platform being used for the intervention, brevity, its speed and ease will allow for greater audience engagement.

II. Pilot-testing phase.

Aim 2A. To compare changes in CVRA in RA patients (a) after web-based EI. We hypothesize that 20% increase in overall CVRA (measured using standardized survey) at 2-3 months post intervention; (b) with and without web-based EI. We hypothesize significantly greater improvement in overall CVRA among RA patients with EI as compared to non EI group, at 2-3 months.

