For patients (a) Overall CVRA (ORA), (b) Traditional CVR awareness (TRA) (c) RA CVR awareness (RARA) will be calculated. Awareness of all 18 CVR being tested (listed in section 1) will denote 100% CVR awareness. To score ORA, patient's correct responses denoting awareness to each of the 18 CVR being tested will be calculated in percentage of total responses. Domain-specific CVR awareness for traditional CVR (TRA) and RA (RARA) will be scored separately using the same strategy.

CALL AND AND A

Paired t tests to compare pre and post (Follow up 2) patient overall CVRA for our primary outcome of interest will be performed. Effect size of gains in overall CVRA for RA patients after EI (Follow up survey 2 and baseline) will be calculated. We will then compare percent change in overall CVRA rates (between baseline and follow up 2) using chi square analysis, among EI and non-EI patients with RA. A p value of ≤ 0.05 will be considered significant on two tailed tests.

Aim 2B. To explore changes in cardiovascular risk screening (CVRS) at the primary health care visits among RA patients with and without EL.

The medical records of RA patients with and without EI will be reviewed in electronic medical record, and analyzed using standardized checklist to assess the prevalence of CVRS and CVD risk reduction plan (meaningful use). Changes in CVRS rates among EI and non EI groups will be calculated, and compared using chi square analysis. A p-value of ≤ 0.05 will be considered significant on two tailed tests.

Exploratory analysis on improvement in PHCP overall CVRA using analysis similar to those discussed for aim 2a will be undertaken, a post hoc power analysis and effect size will be obtained. In addition exploratory univariate and multivariate logistic or linear regression analysis for patient and PHCP correlates of CVRS (baseline) and change in CVRS will be performed. Improvements in Traditional and RA-specific CVRA among RA and PHCPs will be assessed.

J. Dissemination plan: The first step in disseminating outcomes will be to share the results of the study with the participants of the study, RA patients and their PHCP.

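### Aim 2B compares change in provider-performed screening with a chi-square that ignores shared providers, so its p-value may be somewhat too small

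*Protocol*

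**What the plan says.** - **Test.** In I.7, Aim 2B, changes in CVRS rates in the two "groups will be calculated, and compared using chi square analysis", two-tailed, with significance at p of 0.05 or less. I.6 takes "Rates for CVRS at baseline and one year later for all RA patients", so every patient in both groups enters the comparison.
- **Outcome.** Table 1 defines the Aim 2B measure as "Prevalence rates of relevant CVR assessment performed by PHCP among RA patients". It is an act of the provider, read from the patient's chart.
- **Numbers.** Table 4 has a row of "RA patients n=150" for the EI group, another 150 patients without EI, and a PHCP row with n=50 ("n=50 Demographics").
- **Who the PHCPs are.** PHCP inclusion criterion (i), under Data Collection, limits them to providers of EI patients. Criterion (iii) adds "Not providing PHCP to RA patients in the" non-EI group. G.1 gives the purpose, which is to avoid confounding: "Care will be taken to avoid enrollment of PCHPs providing care to RA patients not in the" EI arm. Section F lets the patient name any provider, including the rheumatologist.
- **Two routes of intervention.** PHCPs watch a provider video. EI patients watch their own, whose content in Table 2 includes "Patients role in CVRS".
- **Status.** Section I.1 calls change in CVRS the secondary outcome, and Aim 2B is worded as exploratory. Table 1 nevertheless expects a significant rise.

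**The concern.** Patients who share a PHCP share that provider's screening practice and, if the provider is enrolled, the same exposure to the provider video. Because an enrolled PHCP may not serve non-EI patients, that provider's patients all sit in one arm. In this pattern, a test that assumes independent patients can understate the variance of the arm difference. No other passage adjusts the arm comparison for PHCP: the exploratory regressions look for correlates of CVRS and leave the comparison as it is.

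At stake is how far a nominally significant Aim 2B result can be trusted. There is also a question of interpretation. No passage requires an EI patient's PHCP to enrol or to watch the video, and the planned fidelity summary (mean viewing time) will not show how many EI patients had a PHCP who did.

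**Working it through.** **The plan's own figure.** G.1 gives 127 per group for a 20% improvement in awareness. With two proportions 20 points apart, two-sided alpha 0.05 and 90% power, the formula gives 124 to 130 per group for base rates of 0.30 to 0.50, so 127 reproduces. It belongs to Aim 2A. No sample size or power is stated for Aim 2B, and no design effect appears anywhere.

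**Patients per PHCP.** 150/50 = 3 if all EI patients are covered. At one EI patient per PHCP, 50/150 = 33% are covered; at two, 100/150 = 67%. A mixture is also possible.

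**A test of the 1-year level.** The ICC is not in the protocol and is assumed. Design effect DE = 1 + (m - 1) x ICC, effective n = 150/DE, and actual type I error = 2 x (1 - Phi(1.96/sqrt(DE))). With m = 3 in both arms:

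| ICC | DE | Effective n per arm | Type I error |
|---|---|---|---|
| 0.01 | 1.02 | 147 | 0.052 |
| 0.05 | 1.10 | 136 | 0.062 |
| 0.10 | 1.20 | 125 | 0.074 |
| 0.20 | 1.40 | 107 | 0.098 |

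Simulated (beta-binomial, 150 per arm, rate 45% as an illustration), an uncorrected chi-square on the 1-year level gives 0.069, 0.079 and 0.108 at ICC 0.05, 0.10 and 0.20. Aim 2B does not plan this test; it plans a test of change.

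**A test of change.** Let r be the correlation between a PHCP's underlying screening rate at baseline and at 1 year, and f the correlation between one patient's two results, with the same rate p at both times.

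- Covariance of two patients' changes within a PHCP: 2p(1-p) x ICC x (1 - r).
- Variance of one patient's change: 2p(1-p)(1 - f).
- ICC of change = ICC x (1 - r)/(1 - f).

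If habits are fully stable (r = 1), the ICC of change is 0, DE is 1 and the error is nominal. With r = 0.5 and f near 0, ICCs of 0.05, 0.10 and 0.20 become 0.025, 0.05 and 0.10. Then DE at m = 3 is 1.05, 1.10 and 1.20, and type I error is 0.056, 0.062 and 0.074. Only at r = 0 with f near 0 do the level figures return.

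Simulation of chi-square-type tests of change agrees. With stable PHCP habits, 3 per PHCP and ICC 0.05, 0.10 and 0.20:

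- improved yes/no: 0.052, 0.049, 0.053
- three categories of change: 0.049, 0.050, 0.054
- mean change: 0.049, 0.050, 0.050

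This run assumed that a patient's follow-up result copies baseline with probability 0.3. Across settings, stable habits give about 5-6%. When PHCPs drift over the year, the range is about 5-9%.

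**Larger clusters.** Section B counts 15 rheumatologists, and 150/15 = 10 is an illustrative extreme. At 10 per PHCP with drift, the error for change reaches up to about 20%. A cluster-robust analysis of change held about 5% throughout.

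**The case against.** The strongest reply is that Aim 2B tests change, and a provider's stable habit largely cancels between baseline and follow-up. This stands. A reader might infer a type I error of 6-10% by formula, or 7-11% by simulation, but those figures describe a test of the 1-year level. For change, inflation needs PHCPs to differ in how much they change, and the protocol gives no figure for that. Such differences are nevertheless plausible here, because some PHCPs see a video meant to change their screening and others do not.

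A second reply is that incomplete provider reach is no fault of the test. This also stands. PHCPs are invited by email and take part by consent, so partial uptake is to be expected in a pilot, and comparing all EI with all non-EI patients estimates the effect of the programme as delivered. A reader might go on to infer a specific loss of power from low reach. The documents do not support it: they give neither a provider effect, nor a patient-video effect, nor a CVRS base rate.

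Third, the aim is exploratory. That limits the weight of the point but does not remove it, since the protocol names the test, sets a significance threshold and expects a significant result.

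Criterion (iii) might also be read as the flaw. It is a deliberate guard against contamination and should stay.

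**Conclusion.** The point holds as a minor one. The protocol fixes a patient-level chi-square for change in an outcome that PHCPs produce, while enrolled PHCPs are nested in the EI arm and number 50 for 150 EI patients. Type I error is roughly 5-9% at 3 patients per PHCP if PHCPs differ in how they change, close to nominal if their habits are stable, and more if a few PHCPs carry many patients.

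This rests on an assumed ICC of 0.05-0.20, on similar sharing in the non-EI group (the protocol gives no PHCP count there), and on each PHCP's patients lying within one arm. Where an unenrolled PHCP's patients are split between arms, there is little or no inflation. The point does not reach the primary awareness analysis.

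**What to change.** In I.7, Aim 2B, replace the chi-square with a logistic GEE of CVRS at baseline and 1 year on arm, time and arm-by-time. Use the patient's PHCP as the cluster, robust standard errors and a t reference. The arm-by-time term keeps the planned comparison of change; report the four fitted rates beside it. The model needs a yes/no CVRS status per patient at each time, derived from the checklist.

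A model of 1-year CVRS adjusted for baseline should be a sensitivity analysis at most. No passage states randomisation, and with unequal baselines that model can answer a different question from a comparison of change.

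Keep all patients in their study group whether or not their PHCP took part. Report the share of EI patients whose PHCP viewed the video, as an aid to interpretation only. Leave criterion (iii) unchanged.

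The cost is a change of text in I.7. Table 5 already schedules identification of the PHCP for the chart reviews, and the fidelity monitoring in I.2 already tracks PHCP viewing time. Intervals widen slightly when patients share PHCPs: if the ICC of change were 0.05-0.10 at 3 per PHCP, by a factor of sqrt(1.10) = 1.05 to sqrt(1.20) = 1.10. The model does not restore provider reach; the reported share only makes it visible.
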